2.4.5.4 Analyses of vital sign variables

The summary statistics (including number, mean, median, Q1, Q3, standard deviation, minimum and maximum) of all vital signs variables (values and changes from baseline) will be calculated for each visit or study assessment (baseline, each postbaseline time point, last on-treatment and/or worst on-treatment value) by treatment group. For all parameters, mean changes from baseline with the corresponding standard error will be plotted over time (at same time points) in each treatment group.

The incidence of PCSAs at any time during the treatment-emergent adverse event period will be summarized by treatment group irrespective of the baseline level and/or according to the following baseline status categories:

- Normal/missing
- Abnormal according to PCSA criterion or criteria

2.4.5.5 Analyses of electrocardiogram variables

The summary statistics (including number, mean, median, Q1, Q3, standard deviation, minimum and maximum) of all ECG variables (central laboratory values and changes from baseline) will be calculated for each visit or study assessment (baseline, each postbaseline time point, last on-treatment and/or worst on-treatment value) by treatment group. For all parameters, mean changes from baseline with the corresponding standard error will be plotted over time (at the same time points) in each treatment group.

The incidence of PCSAs at any time during the treatment-emergent adverse event period will be summarized by treatment group irrespective of the baseline level and/or according to the following baseline status categories:

- Normal/missing
- Abnormal according to PCSA criterion or criteria

2.4.6.1.2 Analyses of ADA variables

The following summary will be provided based on ADA population:

- Number (%) of patients with pre-existing immunoreactivity
- Number (%) of patients with treatment-emergent ADA
- The summary statistics (including number, median, Q1, Q3, minimum and maximum) of the peak post-baseline titer for patients with treatment-emergent ADA, and patients with persistent, indeterminate and transient ADA response
- Number (%) of patient with transient treatment-emergent ADA

- Number (%) of patients with persistent treatment-emergent ADA
- Number (%) of patients with indeterminate treatment-emergent ADA
- Number (%) of patients with treatment-boosted ADA
- The summary statistics (including number, median, Q1, Q3, minimum and maximum) of the peak post-baseline titer for patients with treatment-boosted ADA
- The summary statistics (including number, mean, SD, median, Q1, Q3, minimum and maximum) of the ratio of peak post-baseline titer to baseline titer for patients with treatment-boosted ADA
- Listing of ADA peak titer levels and neutralizing antibody status
- Number(%) of patients with neutralizing antibody status

Kinetics of treatment-emergent ADA response

Number (%) of patients with treatment-emergent ADA positive response at each visit will be summarized by each treatment group.

Plot of percentage of patients with treatment-emergent ADA positive response at each visit will be provided by each treatment group.

Impact of ADA on PK

Associations between ADA variables (eg, ADA peak titers, neutralizing antibody status, treatment-emergent, persistent, indeterminate and transient response, treatment-boosted) and serum concentration of dupilumab may be explored for each dupilumab dose group. Plot of serum concentration of functional SAR231893 (REGN668) versus visit will be provided by ADA classifications for each dupilumab dose group. Individual patient plots of PK according to ADA status will be provided to determine which individuals may have had PK impacted by ADAs.

Association of ADA with clinical efficacy endpoints

Associations between the ADA variables (eg, ADA peak titers, neutralizing antibody status, treatment-emergent, persistent, indeterminate and transient response, treatment-boosted) and the primary efficacy endpoint may be explored for the dupilumab dosed group.

Association of ADA with clinical safety endpoints

Association of safety versus ADA status may be analyzed in the ADA population. The safety assessment may focus on the following events:

- Severe injection site reactions last longer than 24 hours or serious injection site reactions
- Hypersensitivity reactions (SMQ (20000214) hypersensitivity narrow search confirmed by medical review)
- Anaphylactic reactions (SMQ (20000021) anaphylactic reaction narrow search)

- In response to AESI like anaphylaxis or hypersensitivity additional ADA samples closer to the event may be analyzed, based on the judgment of the medical investigator and/or medical monitor.
- Associations between ADA variables (eg, ADA peak titers, neutralizing antibody status, treatment-emergent and treatment-boosted) and safety may be explored.

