#### **8.3.1 Adverse event of special interest**

An adverse event of special interest (AESI) is an AE (serious or nonserious) of scientific and medical concern specific to the Sponsor's product or program, for which ongoing monitoring and immediate notification by the Investigator to the Sponsor is required. Such events may require further investigation in order to characterize and understand them. Adverse events of special interest may be added, modified or removed during a study by protocol amendment.

For these AESIs, the Sponsor will be informed immediately (ie, within 24 hours), per SAE notification described in [Section 8.3.2](#), even if not fulfilling a seriousness criterion, using the corresponding pages in the CRF (to be sent) or screens in the e-CRF. If an SAE or any AESI of anaphylactic reactions or systemic allergic reactions that are related to IMP and require treatment, or severe injection site reactions lasting longer than 24 hours, occurs in a patient, blood samples should be collected for determination of functional dupilumab concentration, and ADA assessment at or near the onset and completion of the occurrence of the event, if possible (see [Section 8.5.1.3](#) for details).

- Clinically symptomatic eosinophilia (or eosinophilia associated with clinical symptoms)
- Anaphylactic reactions or systemic allergic reactions that are related to IMP and require treatment (see Appendix 15, [Section 10.15](#))
- Severe injection site reactions that last longer than 24 hours
- Any infection meeting at least one of the following criteria:
  - Any serious infection (SAE)
  - Requires parenteral (intravenous, intramuscular, subcutaneous) antimicrobial therapy

- Requires oral antimicrobial therapy for longer than 2 weeks
- Is a parasitic infection
- Is an opportunistic infection (see Appendix 16, [Section 10.16](#))

Note: antimicrobial therapy refers to antibiotic, antiviral, and antifungal agents

- Significant ALT elevation
  - ALT >5 x the upper limit of normal (ULN) in patients with baseline ALT  $\leq$  2 x ULN; or
  - ALT >8 x ULN if baseline ALT >2 x ULN
- Pregnancy of a female subject entered in a study as well as pregnancy occurring in a female partner of a male subject entered in a study with IMP/NIMP;

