Anaphylactic reaction	Anaphylactic reaction algorithmic approach (Introductory Guide for Standardised MedDRA Queries (SMQs) Version 18.1): includes anaphylactic reaction narrow SMQ (20000021) terms and programmatic identification of cases based on occurrence of at least two preferred terms meeting the algorithm criteria occurring within 24 hours of each other. The latter cases identified using the algorithm will undergo blinded medical review taking into account the timing of events relative to each other and to IMP administration for final determination of an anaphylactic reaction or not.
Hypersensitivity (medically reviewed)	SMQ hypersensitivity (20000214) narrow search or PT in (Pruritus, Pruritus generalized) and [AE corrective treatment/therapy='Y' or Action taken with IMP='Drug withdrawn' or Action taken with IMP='Drug interrupted'] followed by blinded medical review (documented process) for selection of relevant systemic hypersensitivity events
Serious injection site reactions or severe injection site reactions that last longer than 24 hours	HLT = 'Injection site reaction' and either with serious status, or with severe status and (AE end date/time - AE start date/time) ≥ 24 hours or ongoing
Severe or serious infection	Primary SOC = 'Infections and infestations' and with severe or serious status
Parasitic infection	The Infection Type 'Parasitic' was checked on eCRF page "Infection Defined as AESI Complementary Form"
Opportunistic infection	The Infection Type 'Opportunistic' was checked on eCRF page "Infection Defined as AESI Complementary Form"
Drug-related hepatic disorder	Drug-related hepatic disorders-Comprehensive search narrow SMQ (20000006)
Pregnancy	Primary SOC = 'Pregnancy, puerperium and perinatal conditions' or PT in (Aborted pregnancy, False negative pregnancy test, Pregnancy test positive, Pregnancy test urine positive, Ectopic pregnancy termination)
Symptomatic overdose with IMP	Symptomatic Overdose is answered Yes, with Overdose of IMP answered Yes on AE eCRF.
Symptomatic overdose with NIMP	Symptomatic Overdose is answered Yes, with Overdose of NIMP answered Yes on AE eCRF.
Eosinophilia	HLT = 'Eosinophilic disorders' or PT = 'Eosinophil count increased'
Other selected AE grouping	
Injection site reaction	HLT = 'Injection site reaction'
Malignancy	Sub-SMQ (20000091)– Malignant or unspecified tumors
Suicidal behavior	PT in (Completed suicide, Suicidal ideation, Depression suicidal, Suicidal behavior, Suicide attempt)

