2.1.5 Pharmacokinetic variables

Predose serum dupilumab concentrations at Visit 2 (Day 1), dupilumab trough levels at Week 2, Week 4, Week 8, Week 12, Week 16, Week 24, Week 36, Week 52/EOT Visit and posttreatment serum dupilumab at Week 56, Week 60 and Week 64/EOS Visit will be provided.

Anti-dupilumab antibody (ADA) status (negative or titer value, if positive in the ADA assay) at Visit 2 (Day 1), Week 12, Week 24, Week 52 and follow up at Week 64 will be provided. Patients who discontinue early from treatment may be asked to return to the clinic to have additional ADA samples collected for analysis based on the overall clinical presentation at that time.

ADA incidence will be classified as the following:

Pre-existing immunoreactivity are defined as:

An ADA positive response in the assay at baseline with all post treatment ADA results negative, OR an ADA positive response at baseline with all post treatment ADA responses less than 4-fold over baseline titer levels.

Treatment-emergent anti-drug antibodies are defined as:

A positive response in the ADA assay post first dose, when baseline results are negative or missing.

Treatment-emergent ADA responses are further classified as Persistent, Indeterminate or Transient

- a) Persistent Response- defined as a treatment-emergent ADA response with two or more consecutive ADA positive sampling time points, separated by greater than (>) 12-week period (84 days), with no ADA negative samples in between.

- b) Indeterminate Response- defined as a treatment-emergent response with only the last collected sample positive in the ADA assay
- c) Transient Response - defined as a treatment-emergent response that is not considered persistent OR indeterminate

Treatment-boosted response is defined as:

An ADA positive response in the assay post first dose that is greater-than or equal to 4-fold over baseline titer levels, when baseline results are positive.

Titer values (Titer value category)

- Low (Titer <1000)
- Moderate ($1000 \leq \text{Titer} \leq 10\,000$)
- High (Titer >10 000)

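### The exploratory ADA-versus-safety analysis uses narrower anaphylaxis and hypersensitivity definitions than the SAP's own AESI table, and has no rule for ADA samples drawn because of an event

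*SAP*

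**What the plan says.** **The analysis.** SAP 2.4.6.1.2 states: "Association of safety versus ADA status may be analyzed in the ADA population". It names three event types: injection site reactions that are serious, or severe and longer than 24 hours; hypersensitivity by the narrow SMQ confirmed on medical review; and "Anaphylactic reactions (SMQ (20000021) anaphylactic reaction narrow search"). It attaches no test, alpha or decision rule.

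**The AESI definitions.** Table 2 in SAP 2.1.4.1 takes the same narrow SMQ for anaphylaxis and adds "programmatic identification of cases based on occurrence of at least two preferred terms meeting the algorithm criteria occurring within 24 hours" of each other; blinded medical review then decides whether these added cases are anaphylaxis. For hypersensitivity it uses "SMQ hypersensitivity (20000214) narrow search or PT in (Pruritus, Pruritus generalized"), joined to a condition on corrective treatment or on withdrawal or interruption of the drug, again followed by blinded review.

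**ADA sampling.** SAP 2.1.5 schedules ADA "at Visit 2 (Day 1), Week 12, Week 24, Week 52 and follow up at Week 64", which is one baseline and four post-baseline samples. Protocol 1.3.2 adds a sample at the early treatment discontinuation (ETD) visit. For certain events, Protocol 8.3.1 and 8.5.1.3 ask for a drug concentration sample and "ADA assessment at or near the onset and completion of the occurrence of the event, if possible". The SAP's own sentence is "In response to AESI like anaphylaxis or hypersensitivity additional ADA samples closer to the event may be analyzed", on the judgment of the investigator or medical monitor.

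**ADA status.** SAP 2.1.5 defines treatment-emergent ADA as "A positive response in the ADA assay post first dose, when baseline results are negative or missing".

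**The concern.** Protocol 9.4.3 (Table 11) allows the association of ADA with safety to be explored and leaves the detail of the ADA analysis to the SAP, so SAP 2.4.6.1.2 is where that detail belongs. Two things there could mislead a reader of the results.

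First, one SAP carries two definitions of anaphylaxis and two of hypersensitivity, with no reason given. A case can be confirmed as an AESI by blinded review and still be absent from the row of the ADA comparison that bears the same name. If events are few, one or two missing cases can change what the table suggests.

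Second, the events used as outcomes overlap with the events that prompt extra ADA samples. If those samples can set a patient's ADA status, patients with an event have more chances to test positive than patients without one. Ever-positive status and peak titer both rise with the number of samples, even when ADA and the event are unrelated.

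**Working it through.** **Step 1: event definitions side by side.**

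| Event | SAP 2.4.6.1.2 | SAP Table 2 | Result |
|---|---|---|---|
| Anaphylaxis | Narrow SMQ 20000021 | Narrow SMQ 20000021, plus algorithm cases confirmed by blinded review | 2.4.6.1.2 is narrower |
| Hypersensitivity | Narrow SMQ 20000214, medical review | Narrow SMQ 20000214 or pruritus terms, with a treatment/action condition, blinded review | Pruritus route missing from 2.4.6.1.2 |
| Injection site reaction | Serious, or severe and over 24 hours | The same in substance | Match |

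The hypersensitivity entry in Table 2 can be parsed in two ways. If the treatment/action condition applies to pruritus only, 2.4.6.1.2 is simply narrower. If it also applies to the SMQ terms, 2.4.6.1.2 is narrower on pruritus but wider on SMQ events without treatment or drug action. Pruritus is missing from 2.4.6.1.2 under both readings.

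**Step 2: is there a rule for event-triggered ADA samples?**
- SAP 2.1.5: the treatment-emergent definition turns on a positive result after first dose. It does not limit the source of the sample or require it to precede the event.
- SAP 2.3.4: the ADA population needs one reportable post-dose result from any sample.
- SAP 2.5.4: where several results fall in one window, the one closest to target is used, but only for the by-visit summary.
- SAP 2.5.5: the unscheduled-visit rule names laboratory data, vital signs and ECG. It does not name ADA.

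No text excludes triggered samples from ADA status. Read literally, 2.1.5 includes them.

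**Step 3: how large could the sampling effect be?** The documents give no figure to reproduce, so this is an illustration. From the documents: 4 scheduled post-baseline samples, and up to 2 triggered samples per event (onset and completion). Assumed, and not in the documents: positivity p of 1-5% per sample, and no true link between ADA and the event.

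For independent samples, P(ever positive) = 1 − (1 − p)^n. The odds ratio compares n = 5 or 6 with n = 4.

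| p | n = 4 | n = 5 | n = 6 | OR, 5 vs 4 | OR, 6 vs 4 |
|---|---|---|---|---|---|
| 1% | 3.94% | 4.90% | 5.85% | 1.26 | 1.52 |
| 2% | 7.76% | 9.61% | 11.42% | 1.26 | 1.53 |
| 5% | 18.55% | 22.62% | 26.49% | 1.28 | 1.58 |

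Example at p = 2%, n = 6 against 4: (0.1142/0.8858) / (0.0776/0.9224) = 1.53.

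For samples with within-patient correlation ρ (beta-binomial), P(ever positive) = 1 − ∏(b + i)/(a + b + i) for i = 0 to n − 1, with a = p(1 − ρ)/ρ and b = (1 − p)(1 − ρ)/ρ. The odds ratios over p = 1-5% are:

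| ρ | One extra sample | Two extra samples |
|---|---|---|
| 0 | 1.26-1.28 | 1.52-1.58 |
| 0.3 | 1.14-1.15 | 1.26-1.28 |
| 0.6 | 1.08 | 1.14-1.15 |

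The odds ratio is 1.00 if positivity is fully persistent, or if every patient is classified from the same four scheduled samples.

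**The case against.** **Stakes.** The analysis is optional and descriptive, and every Table 2 case still appears in the AESI summaries of SAP 2.4.5.1. The last item in 2.4.6.1.2 also allows ADA to be explored against safety in general, and a case missing from the anaphylaxis row might still appear under hypersensitivity. All of this stands and limits the importance of the point. It does not explain why one SAP holds two definitions of the same event.

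**A stronger reading of the sampling text.** A reader might infer that the SAP counts event-triggered samples in ADA status and that affected patients must be sampled. The text does not go that far. The SAP says such samples may be analyzed and is silent on whether they set a patient's class. SAP 2.1.5 introduces ADA status at named visits before giving the definitions. The protocol says samples should be collected, if possible. The defect is a missing rule.

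**The contrast in sample numbers is uncertain.** Read literally, the protocol trigger begins with any SAE, so patients without an allergic event may also be sampled more often. Not every hypersensitivity event in 2.4.6.1.2 meets the trigger wording. Treated, drug-related anaphylactic or systemic allergic reactions are among the discontinuation criteria in Protocol 7.1.1, so those patients may provide fewer later scheduled samples. Samples at onset and completion of one acute event are also unlikely to be independent. All of this stands: 1.52-1.58 is an upper illustration.

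**Scheduled samples only would also do harm.** Restricting to Weeks 12, 24, 52 and 64 would discard the ETD sample, could leave a patient who reacts early without any classifying result, and could class a patient as negative who was positive at the reaction. This stands, and is why the restricted version should be shown beside the full one and not replace it.

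**Conclusion.** The definition mismatch is in the text. For anaphylaxis, 2.4.6.1.2 omits the algorithm cases that Table 2 accepts after blinded review; for hypersensitivity, it omits pruritus with treatment, withdrawal or interruption. Confirmed AESI cases can drop out of the matching row, but the number cannot be derived from the documents. It would be wrong to say that all the event definitions are narrower, because the injection site reaction definitions agree.

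The sampling point is secondary. The plan does not state that triggered samples count, but the literal definition of treatment-emergent ADA would admit them. Under no true link and 1-5% positivity, the spurious odds ratio is about 1.26-1.28 for one extra independent sample and 1.52-1.58 for two, falling to 1.08-1.15 at correlation 0.6 and to 1.00 with full persistence. Positivity, correlation and the number of extra samples actually drawn are assumptions. Nothing here touches the primary or key secondary conclusions.

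**What to change.** 1. In SAP 2.4.6.1.2, replace the two SMQ definitions with a reference to anaphylaxis and hypersensitivity as defined in Table 2. While doing so, make clear whether Table 2's treatment/action condition covers pruritus only or the SMQ terms as well.
2. Flag each ADA sample as protocol-scheduled (including the ETD sample), event-triggered, or taken on request after discontinuation.
3. Show the ADA-safety association twice: with ADA status and peak titer from protocol-scheduled samples, and from all samples. State that the ETD sample may itself follow from an event, so the scheduled version reduces the sampling imbalance but may not remove it entirely.
4. List triggered and on-request results by case, with timing relative to the event.

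The cost is SAP wording, one sample flag, one extra table and a short listing. No new data are collected and no result is discarded.

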2.4.6.2 Pharmacodynamics/genomics analyses

All biomarkers listed in [Section 2.1.6](#) will be summarized in the Safety population defined as patients who actually received at least 1 dose or part of a dose of the IMP. Baseline values will be the last value collected prior to the first IMP. Descriptive statistics (including number, mean, SD, median, Q1, Q3, min, max) of biomarkers at baseline will be summarized.

Summary plots (mean +/- standard error of the mean) on values at each visit, absolute changes from baseline and percent changes from baseline will be provided for each biomarker by treatment group and visit.

Exploratory analysis of DNA/RNA will be addressed in a separate document.

2.4.7 Analyses of health economics variables

Analyses of healthcare resource utilization will be performed outside of CSR under the responsibility of the Health Economics Outcomes Research (HEOR) department of Sanofi.

2.5 DATA HANDLING CONVENTIONS

2.5.1 General conventions

The following formulas will be used for computation of parameters.

Demographic formulas

Age is calculated as:

$$\text{Integer part of (informed consent date - birth date) / 365.25}$$

Age of onset of COPD is calculated as:

$$\text{Integer part of (COPD diagnosis date - birth date) / 365.25}$$

BMI is calculated as:

$$\text{Weight in kg} / (\text{height}^2 \text{ in meters})$$

Smoking quantity (pack-year) is calculated as following:

$$\text{Number of pack-year} = (\text{packs smoked per day}) \times (\text{years as a smoker})$$

Renal function formulas

For patients ≥ 18 years old, creatinine clearance (CLcr) value will be derived using the equation of Cockcroft and Gault:

$$\text{CLcr (ml/min)} = (140 - \text{age}) \times \text{weight (kg)} \times (1 - 0.15 \times \text{sex (0-M, 1-F)}) / (0.814 \times \text{creatinine } (\mu\text{mol/l}))$$

CLcr will be calculated using the last weight measurement on or before the visit of the creatinine measurement and age at the lab sampling date. Here age is calculated as following:

$$\text{Age} = \text{integer part of (lab sampling date - birth date)/365.25}$$

2.5.2 Data handling conventions for secondary efficacy variables

Periodical average of daily efficacy endpoints at designated study days

For the daily efficacy endpoints, the time period used to calculate the periodical average at each designated study day is summarized in [Table 5](#).

Randomization day is used as the reference day (Day 1).

Table 5 - Periodical average of daily efficacy assessment

Time point	EXACT, E-RS:COPD
Day 8 (Week 1)	2-8
Day 15 (Week 2)	9-15
Day 22 (Week 3)	16-22
Day 29 (Week 4)	23-29
Day 36 (Week 5)	30-36
Day 43 (Week 6)	37-43
...	...
Day 365 (Week 52)	359-365
...	...
Day 449 (Week 64)	443-449

